# 7.5 Withdrawal of informed consent for donated biological samples

If a patient withdraws consent to the use of donated biological samples, the samples will be disposed of/destroyed, and the action documented. If samples are already analyzed, AstraZeneca is not obliged to destroy the results of this research.

As collection of the biological samples is an optional part of the study, then the patient may continue in the study.

The PI:

- Ensures patients' withdrawal of informed consent to the use of donated samples is notified immediately to AstraZeneca or its representative.
- Ensures that biological samples from that patient, if stored at the study site, are immediately identified, disposed of/destroyed, and the action documented.
- Ensures the laboratory(ies) holding the samples is/are informed about the withdrawn consent immediately and that samples are disposed/destroyed, the action documented, and the signed document returned to the study site.
- Ensures that the patient and AstraZeneca or its representatives are informed about the sample disposal.

AstraZeneca or its representatives ensures the central laboratory(ies) holding the samples is/are informed about the withdrawn consent immediately and that samples are disposed of/destroyed and the action documented and returned to the study site.

# 8. ETHICAL AND REGULATORY REQUIREMENTS

# 8.1 Ethical conduct of the study

The study will be performed in accordance with ethical principles that have their origin in the Declaration of Helsinki and are consistent with International Conference on Harmonisation (ICH)/Good Clinical Practice (GCP), applicable regulatory requirements, and the AstraZeneca policy on Bioethics and Human Biological Samples.

# 8.2 Subject data protection

The ICF will incorporate (or, in some cases, be accompanied by a separate document incorporating) wording that complies with relevant data protection and privacy legislation.

AstraZeneca will not provide individual genotype results (collected in study D3820C00004) to patients, any insurance company, any employer, their family members, general physician, or any other third party, unless required to do so by law.

Extra precautions are taken to preserve confidentiality and prevent genetic data being linked to the identity of the patient. In exceptional circumstances, however, certain individuals might see both the genetic data and the personal identifiers of a patient. For example, in the case of a medical emergency, an AstraZeneca Physician or an investigator might know a patient's identity and also have access to his or her genetic data. Also, regulatory authorities may require access to the relevant files, though the patient's medical information and the genetic files would remain physically separate.

# 8.3 Ethics and regulatory review

An Independent Ethics Committee (IEC)/Institutional Review Board (IRB) should approve the final study protocol, including the final version of the ICF and any other written information and/or materials to be provided to the patients. The investigator will ensure the distribution of these documents to the applicable IEC/IRB, and to the study site staff.

The opinion of the IEC/IRB should be given in writing. The investigator should submit the written approval to AstraZeneca or its representative before enrollment of any patient into the study.

The IEC/IRB should approve all advertising used to recruit patients for the study.

AstraZeneca or its representative should approve any modifications to the ICF that are needed to meet local requirements.

If required by local regulations, the protocol should be re-approved by the IEC/IRB annually.

Before enrollment of any patient into the study, the final study protocol, including the final version of the ICF, is approved by the national regulatory authority or a notification to the national regulatory authority is done, according to local regulations.

AstraZeneca or its representative will handle the distribution of any of these documents to the national regulatory authorities.

AstraZeneca or its representative will provide Regulatory Authorities, IECs/IRBs, and PIs with safety updates/reports according to local requirements, including Suspected Unexpected Serious Adverse Reactions (SUSARs), where relevant.

Each PI is responsible for providing the IEC/IRB with reports of any serious and unexpected adverse drug reactions from any other study conducted with the IP. AstraZeneca or its representative will provide this information to the PI so that he/she can meet these reporting requirements.

### 8.4 Informed consent

The PI(s) at each center will:

- Ensure each patient is given full and adequate oral and written information about the nature, purpose, possible risk, and benefit of the study.
- Ensure each patient is notified that they are free to discontinue from the study at any time.
- Ensure that each patient is given the opportunity to ask questions and allowed time to consider the information provided.
- Ensure each patient provides signed and dated ICF before conducting any procedure specifically for the study.
- Ensure the original, signed ICF is stored in the investigator's Study File.
- Ensure a copy of the signed and dated ICF is given to the patient.
- Ensure that any incentives for patients who participate in the study as well as any provisions for patients harmed as a consequence of study participation are described in the ICF that is approved by an IEC/IRB.

# 8.5 Changes to the protocol and informed consent form

Study procedures will not be changed without the mutual agreement of the PI and AstraZeneca.

If there are any substantial changes to the study protocol, then these changes will be documented in a study protocol amendment and where required in a new version of the study protocol (Revised CSP).

The amendment is to be approved by each IEC/IRB and if applicable, also the national regulatory authority, before implementation. Local requirements are to be followed for revised protocols.

AstraZeneca will distribute any subsequent amendments and new versions of the protocol to each PI. For distribution to the IEC/IRB, see Section 8.3.

If a protocol amendment requires a change to a center's ICF, AstraZeneca and the center's IEC/IRB are to approve the revised ICF before the revised form is used.

If local regulations require, any administrative change will be communicated to or approved by each IEC/IRB.

# 8.6 Audits and inspections

Authorized representatives of AstraZeneca, a regulatory authority, or an IEC/IRB may perform audits or inspections at the center, including source data verification. The purpose of an audit or inspection is to systematically and independently examine all study-related activities and documents, to determine whether these activities were conducted, and data were recorded, analyzed, and accurately reported according to the protocol, GCP, guidelines of the ICH, and any applicable regulatory requirements. The investigator will contact AstraZeneca or its representative immediately if contacted by a regulatory agency about an inspection at the center.

# 9. STUDY MANAGEMENT BY ASTRAZENECA

# 9.1 **Pre-study activities**

Before the first patient is entered into the study, it is necessary for a representative of AstraZeneca to visit the investigational study site to:

- Determine the adequacy of the facilities.
- Determine availability of appropriate patients for the study.
- Discuss with the investigator(s) (and other personnel involved with the study) their responsibilities with regard to protocol adherence, and the responsibilities of AstraZeneca or its representatives. This will be documented in a CSA between AstraZeneca or its representative and the investigator.

# 9.2 Training of study site personnel

Before the first patient is entered into the study, an AstraZeneca representative or its representative will review and discuss the requirements of the CSP and related documents with the investigational staff and also train them in any study-specific procedures, the SitePad device, and other system(s) utilized.

The PI will ensure that appropriate training relevant to the study is given to all of these staff, and that any new information relevant to the performance of this study is forwarded to the staff involved.

The PI will maintain a record of all individuals involved in the study (medical, nursing, and other staff).

# 9.3 Monitoring of the study

During the study, an AstraZeneca representative or its representative will have regular contacts with the study site, including visits to:

• Provide information and support to the investigator(s).

- Confirm that facilities remain acceptable.
- Confirm that the investigational team is adhering to the protocol, that data are being accurately and timely recorded in the eCRFs, that biological samples are handled in accordance with the Laboratory Manual, and that study drug accountability checks are being performed.
- Perform source data verification (a comparison of the data in the eCRFs with the patient's medical records at the hospital or practice, and other records relevant to the study) including verification of informed consent of participating patients. This will require direct access to all original records for each patient (eg, clinic charts).
- Ensure withdrawal of informed consent to the use of the patient's biological samples is reported and biological samples are identified and disposed of/destroyed accordingly, and the action is documented, and reported to the patient.

The AstraZeneca representative or its representative will be available between visits if the investigator(s) or other staff at the center needs information and advice about the study conduct.

#### 9.3.1 Source data

Refer to the CSA for location of the source data.

# 9.4 Study agreements

The PI at each center should comply with all the terms, conditions, and obligations of the CSA, or equivalent, for this study. In the event of any inconsistency between this CSP and the CSA, the terms of the CSP shall prevail with respect to the conduct of the study and the treatment of patients and in all other respects, not relating to study conduct or treatment of patients, the terms of the CSA shall prevail.

Agreements between AstraZeneca and the PI should be in place before any study-related procedures can take place, or patients are enrolled.

Prior to a patient's enrollment in the study and any study-related procedures are undertaken, the following should be fulfilled:

- Signed CSA between AstraZeneca and the PI/study center
- Signed CSP and other agreements between AstraZeneca and the PI/study center
- Written approval of the study by the IEC/IRB
- Signed and dated Financial Disclosure forms

### 9.4.1 Archiving of study documents

The investigator follows the principles outlined in the CSA.

# 9.5 Study timetable and end of study

The end of the study is defined as "the last visit of the last patient undergoing the study." The end of study definition is for the entire study.

The study is expected to start in

and to end by

The study may be terminated at individual centers if the study procedures are not being performed according to GCP, or if recruitment is slow. AstraZeneca may also terminate the entire study prematurely for other reasons such as if concerns for safety arise within this study or in any other study with NKTR-118.

# 10. DATA MANAGEMENT BY ASTRAZENECA

### **10.1** Electronic case report form

The eCRF and the protocol are both confidential. The eCRF will be created by the CRO and programmed into the eDC system. All study sites will need internet access to access the eCRFs and will only have access to data for patients at their own study sites. Data management (DM) and other co-ordinator teams will have access to data at all study sites.

All eCRFs are to be completed by an authorized member of the investigational staff and reviewed and signed by the investigator. All entries, corrections, and alterations are to be made by the responsible investigator or an authorized member of the investigational staff. All eCRFs are to be completed in a manner that ensures accurate interpretation of data.

It is each investigator's responsibility to ensure that all discontinued orders or changes in the study or other medications entered on the patient's eCRF correspond to the entries on the patient's medical records.

The eCRFs for any patient leaving the study should be completed at the time medication is terminated for whatever reason.

The eCRFs must accurately reflect data contained in patient's records (eg, source documents).

# 10.2 Data flow

After data are entered into the eCRF by the study site, autoqueries that are generated by the eDC system should be addressed by the study site. Data queries will be raised for inconsistent, impossible, or missing data. All entries to the study database will be available in an audit trail.

Data entered in the eDC system will be immediately saved to a central database and changes tracked to provide an audit trail. When the PI has signed the eCRF electronically as per eCRF instructions, then the patient's data will be locked.

The data collected through third party sources will be obtained and reconciled against study data.

The data will be validated as defined in the DM Plan. Quality control procedures will be applied to each stage of data handling to ensure that all data are reliable and have been processed correctly.

At the monitoring visit, the Study Monitor must perform the Source Document Verification (SDV) of the required fields on completed forms and if there are no open queries, freeze the form. Data management will run manual consistency checks outside of the eDC system and will raise manual queries for study sites to address; if the form is frozen, DM will unfreeze to allow study sites to amend data. The same process is to be followed by any other groups creating manual queries in the eDC system (eg, for SAE reconciliation). Once all data are entered, SDV complete on required fields, manual queries and electronic data reconciliation complete, and all queries closed, then the casebook can be signed. Once the casebook is signed, DM will then lock the casebook so that no amendments can be made.

# 10.3 Database lock

When all data have been coded, validated, signed, and locked, a clean file will be declared. Any treatment revealing data may thereafter be added and the final database will be locked.

Once all patient casebooks are locked, the final data transfer can be sent to statistics. A database lock checklist will also be completed by DM and the programmer to confirm all applicable quality control checks were performed.

# 10.4 Coding

All AEs and medical/surgical histories recorded in the eCRF will be coded using MedDRA. All medications will be classified according to the AstraZeneca Drug Dictionary (AZDD). All coding will be performed by the CRO. The coding will occur outside of the eDC system and will be merged with the clinical datasets sent to statistics.

# **10.5** Investigator site file

At the beginning of the study, an investigator's study file will be established at the study center. The investigator/institution is responsible for maintaining the study documents as specified in the guideline for ICH GCP (Committee for Proprietary Medicinal Products [CPMP]/ICH/135/95) and as required by the applicable regulatory requirement(s). The investigator/institution must take measures to prevent accidental or premature destruction of these documents.

## **10.6 SAE** reconciliation

The CRO will perform SAE reconciliation between the CRO Clinical Study database and the AstraZeneca Clinical Patient Safety database.

## 10.7 ECG data

ECG data will be processed by a central laboratory and the results will be sent electronically to AstraZeneca or its representative.

# 11. EVALUATION AND CALCULATION OF VARIABLES

## **11.1** Calculation or derivation of efficacy variable(s)

## 11.1.1 PAC-SYM

For the PAC-SYM, each item is scored as 0=absence of symptom, 1=mild, 2=moderate, 3=severe, and 4=very severe. The 12 items of the PAC-SYM are assigned to 3 domains:

- Abdominal symptoms (items 1 to 4)
- Rectal symptoms (items 5 to 7)
- Stool symptoms (items 8 to 12).

Each domain score will be calculated as the mean of the non-missing items for that domain. The total score will be calculated as the mean of all non-missing items. If more than 50% of values for a domain or the total score are missing for a visit, the values for that score will be set to missing.

Change from baseline in the PAC-SYM domain and total scores will be calculated for Weeks 4, 12, and 14 as the post-baseline value minus the baseline value. Negative changes from baseline indicate improvement.

The primary baseline PAC-SYM values will be defined as the latest non-missing value collected prior to the first dose of study drug in the previous pivotal study (D3820C00004) (screening, Visit 1 or Week 0, Visit 3), and supportive baseline PAC-SYM values will be defined as the data collected at Visit 8 from the previous study D3820C00004 (also defined as Visit 1 of this study).

## 11.1.2 **PAC-QOL**

For the PAC-QOL, each of the 28 items is scored from 0 to 4. For items 18, 25, 26, 27, and 28, higher scores represent better outcomes. The scores for these items will be reversed (reversed score=4-original score), so that higher scores represent worse outcomes for all items. The 28-item PAC-QOL is divided into 4 subscales:

• Physical discomfort (items 1 to 4)

- Psychosocial discomfort (items 5 to 12)
- Worries/concerns (items 13 to 23)
- Satisfaction (items 24 to 28).

For each visit, individual subscale scores will be calculated as the mean of the non-missing items for that subscale. The total score will be calculated as the mean of all non-missing items. If more than 50% of values for a subscale score or the total score are missing for a visit, the values for that score will be set to missing.

Change from baseline in the PAC-QOL subscale and total scores will be calculated for Weeks 4, 12, and 14 as the post-baseline value minus the baseline value. Negative changes from baseline indicate improvement.

The primary baseline PAC-QOL values will be defined as the latest non-missing value collected prior to the first dose of study drug in the previous pivotal study (D3820C00004) (screening, Visit 1 or Week 0, Visit 3), and supportive baseline PAC-QOL values will be defined as the data collected at Visit 8 from the previous study D3820C00004 (also defined as Visit 1 of this study).

## **11.2** Calculation or derivation of safety variable(s)

## 11.2.1 Adverse events

A treatment-emergent adverse event (TEAE) is defined as any AE that started on or after the first dose of study drug up to the last dose of study drug. An AE already present at the time of the first dose of study drug that worsens in intensity following exposure to study drug or an AE with an unknown/not reported onset date will also be considered as treatment-emergent. Adverse events occurring after the last dose of study drug will also be summarized, which among other purposes, may assess any potential withdrawal-type effects.

Time to onset of an AE (in days) will be calculated as:

AE start date - Date of the first dose of study drug + 1.

Duration of an AE (in days) will be calculated as:

AE resolution date - AE start date + 1.

## 11.2.2 NRS for pain

The 11-point NRS for pain ranging from 0 (no pain) to 10 (worst imaginable pain) will be reported based on the average pain experienced during the 7 days before the study visit. Change from baseline in average NRS values will be calculated for Weeks 4, 8, and 12 as the post-baseline value minus the baseline value. Negative changes from baseline indicate improvement.

The NRS (7-Day recall) collected at Visit 1 will serve as the NRS baseline value.

## 11.2.3 Daily opioid dose

Opioid doses will be recorded for each patient, including both the maintenance dose and dosing for breakthrough pain. However, the daily opioid dose in morphine equivalents (mg/day) will be calculated using only the maintenance dosing information. The mean daily opioid dose (mg/day) for an interval will be calculated as the sum of daily opioid doses (mg/day) for the interval divided by the number of days within the interval in which the data were collected. The mean daily opioid dose will be calculated for the following time intervals: enrollment in this study to Week 4 and Week 4 to Week 12, as well as randomization in the previous pivotal study (D3820C00004) to Weeks 4 and 12 in this study.

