#### **Outcome variable(s):**

- Safety
  - Incidence, nature, and intensity of adverse events (AEs), treatment-related AEs, serious adverse events (SAEs), AEs leading to discontinuation, and specific safety areas of interest
  - Change from baseline in mean daily prescribed opioid dose
  - Mean bisacodyl dose per week
  - Change from baseline in Numeric Rating Scale (NRS) pain score
  - Observed and change from baseline in composite score of modified Himmelsbach scale
  - Changes in vital signs and physical examination
  - Changes in laboratory assessments (ie, chemistry, hematology, and urinalysis [U/A])
  - Changes in electrocardiograms (ECGs)
- Efficacy

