NKTR-118 was well-tolerated in the Phase II study at 5 and 25 mg/day with the most commonly reported side effects being GI in nature (abdominal pain, diarrhea, and nausea) and most frequent in the 50 mg cohort. The frequency of any GI AE was 53% in the 25 mg/day dose group and 48% in the corresponding placebo group. In the 50 mg/day dose group, the GI AE frequency was 69% and 27% in the corresponding placebo group. In the 5 mg/day dose group, the frequency was 46% and 34% in the corresponding placebo group. Most of the AEs were rated mild or moderate. During the double-blind phase, a total of 12 patients discontinued the treatment permanently due to AEs (10 patients in the 50 mg dose group, 1 patient in the 25 mg/day dose group, and 1 patient in the 5 mg/day dose group). Most of the discontinuations were due to GI AEs. There was 1 serious adverse event (SAE) of upper abdominal pain in the 50 mg dose cohort, which was considered to be related to the study drug by the investigator. The patient was briefly monitored in a hospital setting due to this event, which resolved spontaneously without medical sequelae. No reversal of analgesia was seen at any dose in Phase II, as measured by changes in the daily opioid dose or by Numeric Rating Scale (NRS) for pain. A significant increase in total Clinical Opioid Withdrawal Scale (COWS) score for the NKTR-118 50 mg group was noted as compared with placebo at Day 1 of the double-blind treatment period. When the GI component of the COWS instrument (eg, diarrhea, abdominal cramps) was removed from calculation of total COWS scores, there was no longer a significant difference, indicating a lack of increase in the components of the scale that reflect CNS withdrawal. Although these data suggest that the risk for reversal of analgesia or precipitation of opioid withdrawal is unlikely, it is recommended that investigators remain vigilant regarding this potential effect of NKTR-118.

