Routine laxative use is prohibited during the treatment period, since these medications could confound the efficacy of NKTR-118. However, patients who do not respond to NKTR-118 or who are receiving placebo may take a laxative rescue medication if a BM has not occurred within at least 72 hours. In such cases, bisacodyl has been chosen as a first-line treatment because it is efficacious and suitable for as needed administration. Further guidance is provided on the use of bisacodyl as well as an enema if bisacodyl is ineffective.

To minimize confounding influences, an effort has been made to exclude patients with constipation or diarrhea for reasons other than OIC.

NKTR-118 is expected to improve the symptoms of OIC by blocking the peripheral effects of opioid medication without inducing central opioid withdrawal symptoms or interfering with analgesia. Although there was no indication of opioid withdrawal symptoms or reversal of analgesia in the Phase II study, the current study includes the modified Himmelsbach scale to assess withdrawal symptoms, and the NRS along with ongoing assessment of daily opioid dose to assess pain.

The C-SSRS is included as a safety measure to assess risk for suicidality in this patient population.

Although Phase II data did not show changes in liver enzymes, liver function tests will be monitored at study visits, and specific guidelines for handling possible elevations in liver enzymes are included in the protocol.

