# 5.6 **Concomitant and post-study treatment(s)**

Throughout the study, investigators will be encouraged to maintain a patient's baseline pain control regimen, with dose adjustments made as needed in accordance with the patient's clinical needs. Investigators will retain latitude in making these adjustments as clinically indicated, but it is recommended that the guidelines for the ongoing management of pain in the study reference manual (Chou et al 2009) serve as a framework for dose adjustments on-study. It is anticipated that the majority of the patients in this study will be receiving a long-acting opioid for control of background pain and an immediate-release opioid as needed (PRN) for breakthrough pain, although some may be receiving only a short-acting opioid on a scheduled basis.

It is recognized that some patients may have their pain managed by personal physicians who are not connected with the study. In these cases, patients will be asked to notify their personal physicians of their participation in the study, and to ask their physicians to notify the study investigator should a change in their pain control regimen be made.

Concomitant non-opioid analgesics will not be prohibited, but investigators will be encouraged to maintain such drugs at stable doses on-study if possible.

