#### 6.3.1 Safety variables

Safety variables include:

- Incidence, nature, and intensity of AEs, treatment-related AEs, SAEs, AEs leading to discontinuation, and specific safety areas of interest.
- Mean daily opioid dose for Weeks 4 and 12.
- Mean bisacodyl dose per week for Weeks 4 and 12.
- Change from baseline in the mean NRS pain score for Weeks 4, 8, and 12.
- Observed values and change from baseline in composite score in modified Himmelsbach scale for the evaluation of centrally mediated opioid withdrawal symptoms at Week 12.
- Changes in vital signs and physical examination.

- Changes in laboratory assessments (ie, chemistry, hematology, and U/A).
- Changes in ECGs.

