#### 6.3.6 Daily opioid dose

Opioid doses will be recorded for each patient and the daily opioid dose in morphine equivalents will be calculated. Daily maintenance opioid dose and breakthrough opioid pain medication will be recorded on eCRFs at study visits. A home diary will be assigned to each patient to facilitate collection of breakthrough opioid pain usage.

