## 12.2.1 Safety analyses

Adverse events will be coded using the MedDRA dictionary. Three sets of AE summaries will be generated: (1) all AEs recorded in the clinical database, (2) all TEAEs (as defined in Section 11.1.1), and (3) AEs occurring after the last dose of study drug.

Number of events and proportions will be tabulated by preferred term and system organ class. An event that occurred 1 or more times on the date of or subsequent to first dose of study drug will contribute one observation to the numerator of the proportion. The denominator of the proportion will comprise all patients in the Safety population. Adverse events will also be summarized by intensity and separately, by causality (as determined by the investigator). Should a patient experience the same preferred term/system organ class within multiple intensity or causality categories, the patient's worst occurrence (most severe/most related) will be retained in the tabulations. Serious AEs and commonly occurring AEs will be summarized in a generally similar manner. Adverse events of special interest may be further summarized and analysis of AEs occurring within specific time periods (eg, after 1 month, after 3 months, etc.) may be considered.

Adverse events, SAEs, AEs leading to death, and AEs leading to study discontinuation will be tabulated for each treatment group. Descriptive statistics for time to onset and duration of select AEs may be summarized by treatment group. Adverse events that could potentially be indicative of centrally mediated opioid withdrawal, abuse potential, and bowel perforation will be identified prior to unblinding and will also be summarized by each treatment group.

The mean daily opioid dose will be summarized by treatment group for the following intervals: enrollment to Week 4 and Week 4 to Week 12, as well as randomization in the previous pivotal study (D3820C00004) to Weeks 4 and 12 in this study. The mean bisacodyl dose per week will be summarized by treatment group using descriptive statistics for the following intervals: enrollment to Week 4 and Week 4 to Week 12. The observed and change from baseline in composite modified Himmelsbach score will be summarized by treatment group at Week 12 using descriptive statistics. The observed score and change from baseline in NRS pain scores (average in the 7 days prior to the study visit) will be summarized by treatment group for Weeks 4, 8 and 12.

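### The daily opioid dose leaves out collected breakthrough use, so it cannot show loss of analgesia managed by extra breakthrough doses; the synopsis also promises a change from baseline that the body never defines

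*Protocol*

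**What the plan says.** **Purpose.** Section 3.2 says that interference with analgesia will be watched through "the NRS along with ongoing assessment of daily opioid dose to assess pain". Section 1.4 reports that Phase II judged reversal of analgesia "as measured by changes in the daily opioid dose or by Numeric Rating Scale (NRS) for pain".

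**Collection.** Section 5.6 expects most patients to take a long-acting opioid plus "an immediate-release opioid as needed (PRN) for breakthrough pain". Section 6.3.6 puts both components on eCRFs at study visits and adds: "A home diary will be assigned to each patient to facilitate collection of breakthrough opioid pain usage". The visit schedules in Section 3.1 ask about both at Visits 1 to 5.

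**Derivation.** Section 11.2.3 acknowledges that both components are recorded and then says that "the daily opioid dose in morphine equivalents (mg/day) will be calculated using only the maintenance dosing information". The result is averaged over two extension intervals (enrollment to Week 4, Week 4 to Week 12) and over two longer intervals that start at randomization in D3820C00004.

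**Analysis.** Section 12.2.1: "The mean daily opioid dose will be summarized by treatment group for the following intervals", followed by the same four intervals. Section 6.3.1 lists "Mean daily opioid dose for Weeks 4 and 12". The synopsis lists something else: "Change from baseline in mean daily prescribed opioid dose".

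**The concern.** There are two separate defects.

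First, the variable omits a component through which lost analgesia could show. Investigators are encouraged to hold the baseline pain regimen (Sections 3.1 and 5.6), and approved breakthrough medication may be taken without prior agreement. A patient whose analgesia weakened could take more as-needed doses, regain pain control, and show both a flat maintenance dose and a flat NRS. The two measures named in Section 3.2 could then miss the same event together. Safety is the primary objective, and Section 1.4 asks investigators to stay alert to this effect.

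Second, the synopsis and the body disagree on whether opioid dose is reported as a change or as a level. The body supplies no baseline from which a change could be computed.

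**Working it through.** The protocol gives no figure to reproduce: the study is descriptive, without testing or a sample size calculation. The check is a comparison of sections, followed by an illustration of size.

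**1. Is breakthrough use summarised anywhere?**
- Section 6.3.1 lists no breakthrough variable.
- Section 11.2.3 excludes it from the dose.
- Section 12.2.1 tabulates only the mean daily opioid dose as derived in 11.2.3.
- The concomitant-medication record excludes opioids (Section 3.1, Table 1), so it is not a second route.

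The answer is no.

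**2. What does the derived variable show if only breakthrough use rises?** Let M be the maintenance dose and B the breakthrough dose, in mg/day of oral morphine equivalents. Total = M + B; planned variable = M. If B rises by d and M is constant, the total rises by d, or d/(M + B) in relative terms, and the planned variable changes by 0. The doses below are assumptions, with M = 100:

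| Breakthrough, mg/day | Rise in total, mg/day | Relative rise | Planned variable |
|---|---|---|---|
| 10 to 15 | 5 | 5/110 = 4.5% | 0 |
| 20 to 30 | 10 | 10/120 = 8.3% | 0 |
| 20 to 40 | 20 | 20/120 = 16.7% | 0 |
| 40 to 80 | 40 | 40/140 = 28.6% | 0 |

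The zero does not depend on the assumed doses; only the size of what is missed does. If M rises instead, the variable moves with it.

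**3. Change or level?**

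| Place | Quantity | Opioid-dose baseline |
|---|---|---|
| Synopsis, outcome variables | change from baseline | none given |
| Section 6.3.1 | mean dose | none |
| Section 11.2.3 | interval means | none |
| Section 12.2.1 | interval means | none |

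Section 11 defines a baseline for the other synopsis variables that are reported as changes: PAC-SYM, PAC-QOL, NRS, Himmelsbach, laboratory tests, physical examination, vital signs and ECG. Opioid dose is the exception.

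**4. Does the general rule in Section 12.2 fill the gap?** Only partly. It defines a primary baseline (last value before first dose in D3820C00004) and a supportive one (Visit 8), and applies change from baseline to safety parameters where appropriate. It does not say that opioid dose is included, and a last single value does not settle the baseline for a mean over an interval.

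**5. Illustration only: what a change score may add.** Half-width of a 95% interval for an arm difference: 1.96 × SD × √(2/n) for levels, with SD replaced by SD × √(2(1 − ρ)) for change. Take n = 630/3 = 210 (equal split assumed) and SD = 80 to 274 mg/day (assumed; the upper value comes from a log-normal whose ±2 SD limits are the eligibility limits of 30 and 1000 mg).
- Levels: 15.3 to 52.3 mg/day.
- Change, ρ = 0.9: 6.8 to 23.4 mg/day.
- Change, ρ = 0.5: no gain.

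The protocol gives neither the SD nor ρ.

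**The case against.** **Maintenance-only is a disclosed choice with a plausible reason.** Regimens are confirmed by prescription or labelled bottle, whereas actual as-needed intake rests on a home diary and is noisier. This stands as a reason to keep the maintenance figure. It does not justify leaving the collected breakthrough data out of every summary.

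**Other checks exist.** NRS change at Weeks 4, 8 and 12, the Himmelsbach scale, withdrawal-type AEs and discontinuation for inadequate pain control all contribute. They narrow the gap without closing it. Breakthrough doses can hold the NRS down, and its baseline is Visit 1, after 12 weeks of treatment. The Himmelsbach scale rates withdrawal signs and is repeated only at Week 12. Day-to-day pain fluctuations are not AEs unless they meet SAE criteria. Discontinuation follows only after reasonable attempts at pain control have failed.

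**The SAP may add detail.** It has not been seen and could add a breakthrough table. The exclusion in 11.2.3 and the mismatch with the synopsis are nevertheless positive statements in the protocol.

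**Stronger readings that a reader might infer, and that the documents do not support:**
- *That opioid dose is not meant to be analysed as change at all.* The synopsis lists change, and Section 12.2 has a general rule. The defect is an inconsistency and a missing baseline.
- *That the variable is insensitive to any loss of analgesia.* Maintenance changes are permitted, must be recorded, and would register.
- *That lost analgesia would appear first as breakthrough dosing.* No section says so; it is one possible route.
- *That the long intervals hide a late change.* A 20 mg/day rise over the last 8 of 24 weeks appears as 20 × 8/24 = 6.7 mg in the interval from pivotal randomization. The Week 4 to Week 12 interval is planned separately and shows the full 20 mg. The long intervals are supplementary.
- *That between-patient spread swamps any within-patient change.* The 30 to 1000 mg range is an eligibility limit, not an observed spread.

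**Conclusion.** The point holds in two limited parts. First, as derived, daily opioid dose is blind to a rise confined to breakthrough use, and no other planned summary shows that use; this follows from the definition and needs no assumption. How much would be missed is unknown: the 4.5% to 28.6% range illustrates assumed doses and is not a prediction. Second, the synopsis and the body conflict on change versus level, and no opioid-dose baseline is defined. The possible precision gain from a change score depends on an assumed SD and correlation and is not part of the case. No test or power is affected, because the study is descriptive. What is at stake is whether the safety tables can support a statement about preserved analgesia.

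**What to change.** Amend the synopsis and Sections 6.3.1, 11.2.3 and 12.2.1 so that they agree on the following:

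1. Keep the maintenance-only mean daily dose as planned.
2. Add descriptive summaries by arm of breakthrough and of total (maintenance plus breakthrough) oral morphine equivalents, using the Appendix E conversions, for enrollment to Week 4 and Week 4 to Week 12.
3. Define the opioid-dose baseline: primary, before the first dose in D3820C00004; supportive, the end of that study (Visit 1 here). Use the pre-pivotal baseline for breakthrough and total dose only if D3820C00004 captured breakthrough use comparably. That study used an eDiary device and this one does not, and how it recorded breakthrough intake is not described here.
4. Report change from baseline for the same two intervals.
5. State whether a diary day without an entry counts as no use or as missing, because 11.2.3 divides by days with data.

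The cost is a few sentences and some programming, with no new data collection in this study. Nothing in patients' pain management changes. The downside is noisier diary data, which is why the new figures should stand beside the maintenance figure and not replace it. Make the change before unblinding, so that the added summaries cannot look selected.
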